9.1.3 Early Termination of Treatment

If a subject prematurely discontinues study drug treatment, an ETT Visit should be scheduled as soon as possible after the decision to discontinue treatment.

If the ETT Visit occurs 3 weeks or later following the last dose of study drug, then the ETT Visit will replace the Safety Follow-up Visit, and a separate Safety Follow-up Visit will not be required.

If a subject withdraws from the study and also withdraws consent or assent, no further assessments will be performed. Vertex may retain and continue to use any data and samples collected before such withdrawal of consent or assent.

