9.8.1 Liver Function Tests

The central laboratory will notify the medical monitor of alanine transaminase (ALT) or aspartate transaminase (AST) $>3 \times$ upper limit of normal (ULN) and total bilirubin $>2 \times$ ULN that are derived from centrally submitted samples.

Subjects with new treatment-emergent ALT or AST elevations of $>3 \times$ ULN, with or without total bilirubin $>2 \times$ ULN, must be followed closely, including confirmatory testing performed by

the central laboratory within 48 to 72 hours of the initial finding and subsequent close monitoring of ALT, AST, and bilirubin levels, as clinically indicated.

If a subject cannot return to the site for confirmatory testing, a local laboratory may be used. Local laboratory results must be reported immediately to the medical monitor, and the subject must have the tests repeated and sent to the central laboratory as soon as possible (ideally within 48 to 72 hours).

Study drug administration **must be interrupted** immediately (prior to confirmatory testing) if any of the following criteria are met:

- ALT or AST $>8 \times$ ULN
- ALT or AST $>5 \times$ ULN for more than 2 weeks
- ALT or AST $>3 \times$ ULN, in association with total bilirubin $>2 \times$ ULN and/or clinical jaundice

A thorough investigation of potential causes should be conducted, and the subject should be followed closely for clinical progression.

Study drug administration **must be discontinued** if the following criteria are met:

- Subsequent ALT or AST values confirm the initial elevation that satisfied the interruption rule (above), and no convincing alternative etiology (e.g., acetaminophen use, viral hepatitis, alcohol ingestion) is identified, regardless of whether transaminase levels have improved

All subjects in whom treatment is discontinued for elevated transaminases (and bilirubin, as applicable) should have these levels monitored closely until levels normalize or return to baseline.

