10.2.2.5 Study Drug Exposure

Study drug exposure summaries will be based on the OLE-SS.

Duration of study drug exposure (in days) will be calculated as [last dose date – first dose date + 1 day] within the OLE Safety Period, regardless of study drug interruption. For subjects who are still on study drug at IA data cutoff date, the corresponding cutoff date will be used as the last dose date for the exposure calculation.

Study drug exposure (in weeks) will be summarized descriptively by the number of subjects (n), mean, SD, median, min, and max. It will also be summarized into the following categories: <=24 weeks, >24 to <=48 weeks, >48 to <=72 weeks, >72 to <=96 weeks, >96 to <=120 weeks, >120 to <=144 weeks, >144 to <=168 weeks, >168 to <=192 weeks, >192 weeks. Additionally, the total study drug exposure, defined as the sum total of the study drug exposure across all subjects (in patient-weeks and patient-years), will be provided.

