Obtain the age at informed consent in “yy, mm” format (e.g., 24 years, 6 months) in parent study from the VS page at the Screening Visit in the parent study.			
Obtain the informed consent date in parent study.			
Then age (in months) at first dose or post-baseline visit = integer part of {[age at informed consent (in months) in parent study + 0.5 + diff(first dose date or post-baseline visit date, informed consent date) in months in parent study]} + 0.5.			
3. Missing first dose date or last dose date			
If the first dose date is missing, use Day 1 visit date.			
If the last dose date of study drug is not available and there is no data to indicate that the subject discontinued treatment, the data cutoff date will be used instead.			
If the subject discontinued treatment and the last dose date is missing or partial date is reported, the last dose date will be imputed based on, in descending order priority, the Early Treatment Termination (ETT) visit date, last visit date before the Safety Follow-up, or the last study drug administration date from EX SDTM domain, as appropriate. The imputation algorithm will ensure the imputed last dose date does not exceed the data cutoff date.			
4. Electrocardiogram:			
Baseline is defined in Section 8.1. If multiple ECG measurements are obtained on the same calendar day during the TE period,			
○ For summary purpose, the average value will be used as the ECG on that day;			
○ For threshold analysis purpose, all ECG values will be used			

Table 13-2 Analysis Visit Windows for Safety and Efficacy Assessments for the OLE study			
Assessment	Visit¹	Target Study Day	Analysis Visit Window (in study days)²
Safety Assessment			
Serum Chemistry	Baseline	1	defined in section 8.1
Hematology	OLE Part A Week 8	57	[1, 85]
Vital Signs (excluding Weight, Height, BMI, and corresponding z-scores) ³	OLE Part A Week 16	113	(85, 141]
	OLE Part A Week 24	169	(141, 211]
	OLE Part A Week 36	253	(211, 295]
	OLE Part A Week 48	337	(295, 379]
	OLE Part A Week 60	421	(379, 463]
	OLE Part A Week 72	505	(463, 547]
	OLE Part A Week 84	589	(547, 631]
	OLE Part A Week 96	673	(631, 715]
	OLE Part B Week 12	757	(715, 799]
	OLE Part B Week 24	841	(799, 883]
	OLE Part B Week 36	925	(883, 967]
	OLE Part B Week 48	1009	(967, 1051]
	OLE Part B Week 60	1093	(1051, 1135]
	OLE Part B Week 72	1177	(1135, 1219]
	OLE Part B Week 84	1261	(1219, 1303]
	OLE Part B Week 96	1345	(1303, 1359]
	Safety Follow-up ⁴	Not applicable	Use nominal visit

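### The rule for a missing or partial last dose date puts the ETT visit ahead of a reported month and the dosing record, so off-drug days can count as exposure; the treatment-emergent period is little affected

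*SAP*

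**What the plan says.** SAP Appendix A, Table 13-1, Derived Variables item 3 sets the rule, and Table 13-2 carries it over to the whole-study analysis. The trigger is "If the subject discontinued treatment and the last dose date is missing or partial date is reported". In that case "the last dose date will be imputed based on, in descending order priority, the Early Treatment Termination (ETT) visit date, last visit date" before Safety Follow-up, "or the last study drug administration date from EX SDTM domain, as appropriate". The only limit is this: "The imputation algorithm will ensure the imputed last dose date does not exceed the data cutoff date".

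Protocol 9.1.3 says "an ETT Visit should be scheduled as soon as possible after the decision to discontinue treatment". It gives no maximum interval from the last dose and provides for a late visit: "If the ETT Visit occurs 3 weeks or later following the last dose of study drug", the ETT visit takes the place of Safety Follow-up.

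Exposure in SAP 10.2.2.5 is "last dose date – first dose date + 1 day] within the OLE Safety Period, regardless of study drug interruption"; SAP 10.2.1.5 does the same for Part A. SAP 9.2 and 9.3 end the safety (treatment-emergent) period at the earlier of 28 days after the last dose and completion of study participation. Protocol 9.1.5 makes the ETT visit the completion date when it replaces Safety Follow-up.

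**The concern.** The order ranks the most direct evidence, the administration record, last. The first choice is a visit timed by the decision to stop, not by the last dose. The two can differ. Under Protocol 9.8.1, for example, drug is interrupted first and discontinuation follows only if "Subsequent ALT or AST values confirm the initial elevation that satisfied the interruption rule", so the last dose can precede the decision.

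The trigger includes partial dates, yet nothing keeps the result inside the part that was reported. The SAP treats other partial dates differently. Appendix B sets a medication stop date that lacks only its day to the end of the reported month, and Appendix D keeps a known month for adverse event start dates.

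The imputed date feeds exposure duration, patient-years, and the denominators of compliance and percentage of tablets taken. It also feeds the exposure-adjusted event rates, if these are divided by this exposure; the SAP does not spell out their denominator. The error arises only in discontinued subjects and runs in one direction whenever the ETT visit follows the last dose. Safety is the primary endpoint.

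**Working it through.** The plan states no figure for this rule, so there is none to reproduce. The check is date arithmetic on the SAP's definitions.

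**Notation.** L = true last dose; d = days from L to the ETT visit; s = days from L to a separate Safety Follow-up visit (28 ± 7, so 21 to 35; Protocol 9.1.2); C = completion of participation. C = L + d if d ≥ 21, because the ETT visit replaces follow-up; otherwise C = L + s.

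**Exposure.** Imputed minus true = (L + d − first dose + 1) − (L − first dose + 1) = d days. Restricting exposure to the safety period does not remove this, because that period is derived from the same imputed date.

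Relative error at d = 21:
- 84 true days: 21/84 = 25.0%
- 168 days: 21/168 = 12.5%
- 672 days (96 weeks): 21/672 = 3.1%
- 1344 days (192 weeks): 21/1344 = 1.6%

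Pooled, against the maximum of 64 × 1344 = 86,016 subject-days (64 enrolled, SAP 7.2):
- one subject at d = 21: 21/86,016 = 0.024%
- four subjects at d = 42: 168/86,016 = 0.195%

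These lags and counts are assumptions, since the documents give neither. Actual total exposure will be below the maximum, so the shares would be somewhat larger, but still small.

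**Percentage of tablets taken.** A fully adherent subject with 84 true days and d = 21 scores 100 × 84/(84 + 21) = 80.0%, exactly the SAP's category boundary. Any longer lag puts that subject below it.

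**Compliance.** The longer denominator raises the percentage for a given number of interruption days.

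**Reported month overridden (illustrative dates).** Last dose 5 March, reported only as March; ETT visit 4 April.
- SAP rule: 4 April, outside the reported month, 30 days late.
- Cap at month end: 31 March, 26 days late.
- EX date, if it holds the true last dose: no error.

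**Treatment-emergent period.** Overstatement = min(L + d + 28, C) − min(L + 28, C).

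| Case | Imputed end | True end | Overstatement |
|---|---|---|---|
| d = 21, ETT replaces follow-up | L + 21 | L + 21 | 0 days |
| d = 28, same | L + 28 | L + 28 | 0 days |
| d = 42, same | L + 42 | L + 28 | 14 days |
| d = 56, same | L + 56 | L + 28 | 28 days |
| d = 14, separate follow-up at s = 28 | L + 28 | L + 28 | 0 days |
| d = 14, separate follow-up at s = 35 | L + 35 | L + 28 | 7 days |

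So where a late ETT visit replaces follow-up, the overstatement is 0 for d from 21 to 28 and d − 28 beyond that. With a separate in-window follow-up visit it is 0 if s ≤ 28, and otherwise the smaller of d and s − 28, at most 7 days. For a subject who moves to another regimen within 28 days of the last dose and whose ETT visit replaces follow-up (Protocol 9.1.2), it is 0.

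**The case against.** A reader might add 21 and 28 and infer that the treatment-emergent period runs at least 49 days past the true last dose. The documents do not support that. The period stops at completion of participation, which is the ETT date in exactly that situation, so at a 21-day lag both the true and the imputed period end on day 21. Protocol 13.1.1.3 also collects adverse events only until completion, which leaves little room for later events to be mislabelled.

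Nor does every ETT visit that replaces follow-up imply at least 21 days of false exposure. The transition route in Protocol 9.1.2 has no 3-week minimum, and the lag there can be zero.

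The defence has further sound points. ETT visits are meant to be prompt. Harm needs a discontinuation, an incomplete last dose date and a lag, all in the same subject. Safety is descriptive, and the pooled effect is tiny. The closing words about using the EX date as appropriate leave some discretion, although they do not say when it should outrank the visit date, so two programmers could derive different dates.

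The strongest point is that ranking EX first has a cost. The documents do not say how complete EX is when the last dose date is missing. If its last dated record were a supervised clinic dose (an assumption), then with clinic visits 8 to 12 weeks apart it could place the last dose up to about 12 weeks early, shorten the treatment-emergent period and drop events. A later date also fits the SAP's convention of classing adverse events of uncertain timing as treatment-emergent. That convention is cautious for counting events. It is not cautious for rates, where a larger denominator lowers the result. None of these points justifies discarding a month that was reported.

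**Conclusion.** The point holds for exposure and for the override of reported data. Each affected subject's exposure is overstated by the full ETT lag: 21 days or more when the visit is 3 weeks or later after the last dose, and nothing when the visit falls on the last dosing day. That can be material for one early discontinuer (25% on 84 days) and for that subject's tablets-taken percentage. It is negligible in the pooled total, at about 0.024% of maximum exposure for one subject at 21 days.

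The effect on the treatment-emergent period is secondary. Where a late ETT visit replaces follow-up, it appears only for lags beyond 28 days. With a separate follow-up visit it is at most 7 days, provided that visit is within its window.

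The number of affected subjects and their lags are not given, so the figures show what the rule permits, not what happened. This is a small correction to a stated rule that can contradict collected data, not a threat to the study's conclusions.

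**What to change.** Replace the priority order in Derived Variables item 3 with the following:

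1. Where a recorded stop date or a complete EX last-administration date exists and agrees with any reported month or year, use it ahead of any visit date.
2. Otherwise, use the latest date consistent with the reported month or year, no later than the ETT visit (or last visit before Safety Follow-up) and no later than the data cutoff.
3. Where nothing was reported and no reliable dosing record exists, use the ETT or last visit date as now.

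State what counts as a complete EX record, so that the choice is no longer left to case-by-case judgement, and query the site where the bounds conflict. Report how many last dose dates were imputed and by which step.

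The cost is one SAP paragraph and one derivation; SAP Section 4 provides for documented revisions before the Week 144 data cutoff. The downside is that EX may be incomplete, and an early EX date could shorten the treatment-emergent period, which is why the visit date stays as the fallback. Keeping the date within a reported month or year costs almost nothing and can be adopted even if EX is not moved up.

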3 SCHEDULE OF ASSESSMENTS

Table 3-1 and **Table 3-2** provide the schedules of assessments. All visits are to be scheduled relative to the Day 1 Visit in each Part.

The Cystic Fibrosis Questionnaire-Revised (CFQ-R) must be completed before any other assessment (except informed consent form [ICF] signing) at relevant clinic visits. Multiple breath washout (MBW) assessments should be performed before spirometry, and ECG should be performed before any assessments that may affect heart rate (such as blood draws). Remaining assessments may be performed in any order when more than 1 assessment is required at a particular time point. All assessments will be performed before study drug dosing (Section [9.6.1](#)), unless noted otherwise.

Table 3-1 Study VX19-445-107: Part A Treatment Period and Safety Follow-up Visit

Event/Assessment ^a	Part A Treatment Period (96 weeks)						Part A ETT Visit ^b	Part A Safety Follow-up Visit ^c (28 ± 7 Days After Last Dose of Study Drug)	Comments
	Day 1 ^d	Weeks 8, 16, 24, 36 (± 5 Days)	Weeks 4, 12, 20, 28, 32, 40, 44, 52, 56, 64, 68, 76, 80, 88, 92 (± 5 Days)	Week 48 (± 5 Days)	Weeks 60, 72, 84 (± 5 Days)	Week 96 ^e (± 5 Days)			
Clinic visit	X	X		X	X	X	X	X	
Telephone contact			X						When telephone contact takes the place of a clinic visit, a urine pregnancy test will be performed with a home kit provided by the study site (Section 11.5.2).
Informed consent and assent	X								
Inclusion and exclusion criteria confirmation	X								See Section 8 for details.
CFQ-R	X	Weeks 8, 24		X	Week 72	X	X	X	To be completed before any other assessments scheduled at relevant visits (Section 11.3.5).
Ophthalmologic examination				X		X	X		Subjects will have an ophthalmologic examination at Week 48 and at Week 96 (Section 11.5.5). In addition, an ophthalmologic examination will be performed at the ETT Visit for subjects who discontinue study drug if the subject has received at least 12 weeks of study drug since their last study ophthalmologic examination.
Full physical examination	X					X	X		Symptom-directed physical examinations will be performed at any time if deemed necessary by the investigator or healthcare provider (Section 11.5.3).
Weight, height, and BMI	X	X		X	X	X	X	X	Weight and height measured with shoes off (Section 11.3.4).

^a All assessments will be performed before study drug dosing unless noted otherwise.

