Blood biomarker sample	X			X		X	X		Section 11.4.2

^e Subjects whose Part B Day 1 Visit is on the same day or within 1 calendar day as the Part A Week 96 Visit do NOT have to repeat any Part B Day 1 assessments that were specified to be performed at the Part A Week 96 Visit. Subjects whose Part B Day 1 Visit is more than 1 calendar day after the Part A Week 96 Visit must complete all assessments specified for the Part A Week 96 AND Part B Day 1 Visits.

Table 3-1 Study VX19-445-107: Part A Treatment Period and Safety Follow-up Visit

Event/Assessment ^a	Part A Treatment Period (96 weeks)						Part A ETT Visit ^b	Part A Safety Follow-up Visit ^c (28 ± 7 Days After Last Dose of Study Drug)	Comments
	Day 1 ^d	Weeks 8, 16, 24, 36 (± 5 Days)	Weeks 4, 12, 20, 28, 32, 40, 44, 52, 56, 64, 68, 76, 80, 88, 92 (± 5 Days)	Week 48 (± 5 Days)	Weeks 60, 72, 84 (± 5 Days)	Week 96 ^e (± 5 Days)			
FE-1	X	Week 24		X		X	X		Samples may be collected by the subject's caregiver up to 24 hours before the study visit (e.g., at home). The sample may be collected pre- or postdose (Section 11.4.1).
IRT	X	Week 24		X	Week 72	X	X		Section 11.4.1
Study drug dosing	Day 1 through evening before Week 96 Visit								Subjects on study drug interruption at the end of the parent study may not begin dosing until they meet the criteria in Section 9.8. Refer to Section 9.6.1 for study drug administration details.
Study drug count		X		X	X	X	X		
Other events related to outcome	Continuous from signing of ICF through completion of study participation								Includes PEx, administration of antibiotic therapy for sinopulmonary signs/symptoms, and hospitalizations for CF (Section 11.3.6). Completion of study participation is defined in Section 9.1.5.
Medications review	Continuous from signing of ICF through completion of study participation								Completion of study participation is defined in Section 9.1.5.
Treatment and procedures review	Continuous from signing of ICF through completion of study participation								Completion of study participation is defined in Section 9.1.5.
AEs and SAEs	Continuous from signing of ICF through completion of study participation								Completion of study participation is defined in Section 9.1.5.

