^d Subjects whose Part B Day 1 Visit is on the same day or within 1 calendar day as the Part A Week 96 Visit do NOT have to repeat any Part B Day 1 assessments that were specified to be performed at the Part A Week 96 Visit. Subjects whose Part B Day 1 Visit is more than 1 calendar day after the Part A Week 96 Visit must complete all assessments specified for the Part A Week 96 AND Part B Day 1 Visits.

Table 3-2 Study VX19-445-107: Part B Treatment Period and Safety Follow-up Visit

Event/Assessment ^a	Part B Treatment Period (96 weeks)					Part B ETT Visit ^b	Part B Safety Follow-up Visit ^c (28 ± 7 Days After Last Dose of Study Drug)	Comments
	Day 1 ^d	Weeks 4, 8, 16, 20, 28, 32, 40, 44, 52, 56, 64, 68, 76, 80, 88, 92 (± 5 Days)	Weeks 12, 36, 60, 84 (± 5 Days)	Weeks 24, 48, 72 (± 5 Days)	Week 96 (± 5 Days)			
Pulse oximetry	X		X	X	X	X	X	Performed after subject has been at rest for at least 5 minutes (Section 11.5.3).
Standard 12-lead ECG	X			X	X	X	X	Performed after subject has been at rest for at least 5 minutes (Section 11.5.4).
Spirometry	X		X	X	X	X	X	Should be performed pre-bronchodilator at approximately the same time at each visit (Section 11.3.1).
Sweat chloride	X			X	X	X		At each time point, 2 samples will be collected (1 sample from each arm; Section 11.3.2).
Pregnancy test (all female subjects)	urine	urine	urine	urine	serum	serum	serum	At telephone contact visits, a urine pregnancy test will be performed with a home kit provided by the study site (Section 11.5.2).
Serum chemistry	X		X	X	X	X	X	Section 11.5.2
Hematology	X		X	X	X	X	X	Section 11.5.2
Coagulation	X			X	X	X	X	Section 11.5.2
Urinalysis	X			Week 48	X	X		Section 11.5.2
Multiple breath washout	X			X	X	X		Performed in multiple replicates, pre-bronchodilator, and before the spirometry assessment (Section 11.3.3).
Blood biomarker sample	X			Week 48	X	X		Section 11.4.2
FE-1	X			Week 48	X	X		Samples may be collected by the subject's caregiver up to 24 hours before the study visit (e.g., at home). The sample may be collected pre- or postdose (Section 11.4.1).
IRT	X			X	X	X		Section 11.4.1

Table 3-2 Study VX19-445-107: Part B Treatment Period and Safety Follow-up Visit

Event/Assessment ^a	Part B Treatment Period (96 weeks)					Part B ETT Visit ^b	Part B Safety Follow-up Visit ^c (28 ± 7 Days After Last Dose of Study Drug)	Comments

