9.1.1 Treatment Period

Treatment Period assessments are listed in [Table 3-1](#) and [Table 3-2](#).

Part A:

Subjects will receive the first dose of study drug on Part A Day 1 after obtaining informed consent (and assent, when applicable) and confirming eligibility. Subjects who enroll in this study on a study drug interruption will NOT receive the first dose of study drug until they meet the resumption criteria in Section [9.8](#); before receiving study drug, subjects will repeat all Part A Day 1 assessments.

Study drug administration details are provided in Section [9.6](#).

Subjects whose Part A Day 1 Visit is NOT within 1 day of the last scheduled visit of the parent study will repeat all Part A Day 1 assessments.

Subjects whose Part A Day 1 Visit is within 1 day of the last scheduled visit of the parent study will NOT have to repeat any Part A Day 1 assessments that were specified to be performed at the last scheduled visit in the parent study.

Part B:

For subjects who elect to enroll in Part B, the Part A Week 96 Visit will be the start of treatment in Part B (i.e., Part B Day 1).

Subjects whose Part B Day 1 Visit is on the same day or within 1 calendar day of the Part A Week 96 Visit do NOT have to repeat any Part B Day 1 assessments that were specified to be performed at the Part A Week 96 Visit. Subjects whose Part B Day 1 Visit is more than 1 calendar day after the Part A Week 96 Visit must complete all assessments specified for the Part A Week 96 AND Part B Day 1 Visits.

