12.3 Statistical Analysis

12.3.1 General Considerations

Continuous variables will be summarized using the following descriptive summary statistics: the number of subjects (n), mean, SD, median, minimum value (min), and maximum value (max). The precision of the measurement for each continuous variable will be specified in the SAP. Unless otherwise specified, min and max values will be reported with the same precision as the units of the raw data. The mean, median, and SD will be reported to 1 additional decimal

place. Any values that require a transformation to standard units (metric or SI) will be converted with the appropriate precision.

Categorical variables will be summarized using counts and percentages. Percentages will be presented to 1 decimal place.

The baseline value, unless otherwise specified, will be the most recent non-missing measurement (scheduled or unscheduled) collected before the first dose of study drug in the parent study. For assessments collected in replicates, the baseline will be defined as the average of non-missing values.

Change (absolute change) from baseline will be calculated as post-baseline value – baseline value.

The **Efficacy Analysis Period** for each Part will include the time from the first dose of study drug to the last scheduled efficacy visit in the corresponding Part, unless otherwise specified.

The **Treatment-emergent (TE) Period** for each Part will include the time from the first dose of study drug to 28 days after the last dose of the study drug or to the date of completion of study participation in the corresponding Part (as defined in Section 9.1.5), whichever occurs first.

Part A and Part B data will be analyzed separately, using the respective analysis set, efficacy analysis period, and TE period for each Part. For analysis of the number of PEx, events in the parent study and this study (Parts A and B, as applicable) may also be combined.

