a. If no numerical measurement is available within a visit window, the measurement will be considered missing for the visit.			
b. If there is more than 1 numerical measurement available within a visit window, use the following rules:			
i. The measurement closest to the target day will be used; or			
ii. If there are multiple measurements with the same distance from the target day, the latest measurement will be used. If the latest measurement cannot be determined, then unscheduled visit will be selected.			
³ For measurement collected on the date of first dose of study drug in Treatment Period, if it cannot be determined whether the measurement is before or after the first dose:			
1. Scheduled measurement will be treated as pre-dose observation.			
2. Unscheduled measurement will be treated as post-dose observation.			
⁴ For safety Assessment, Safety Follow-up analysis visit will be based on nominal Safety Follow-up visit. If a subject doesn't have a nominal Safety Follow-up visit but has an ETT visit with study day >687, then the ETT visit will be mapped into Safety Follow-up analysis visit.			
⁵ For efficacy assessment, if a subject has nominal safety follow up visit with study day >687, then nominal Safety Follow-up visit will be mapped to Safety Follow-up visit; else if subject doesn't have a nominal safety follow-up visit with study day > 687 but has an ETT visit with study day >687, then the ETT visit will be mapped into Safety Follow-up analysis visit; else if there are multiple assessments with >687 then select the earliest record.			
Derived Variables:			

Table 13-1 Analysis Visit Windows for Safety and Efficacy Assessments for Part A			
Assessment	Visit¹	Target Study Day	Analysis Visit Window (in study days)²
1. Age (in years) at first dose date and post-baseline visit (for demographics, listing and the calculation of [percent] predicted spirometry variables):			
Obtain the age at informed consent in “yy, mm” format (e.g., 24 years, 6 months) in parent study from the Vital Signs (VS) page at the Screening Visit in parent study and add 0.5 month to convert to days.			
Obtain the informed consent date in parent study.			
Then age (in years) at first dose or post-baseline visit = [(first dose date or post-baseline visit date – informed consent date in parent study) in days + age at informed consent (in days) in parent study]/365.25.			
2. Age (in months) at first dose date and post-baseline visit (for use in calculation of BMI):			

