Standard 12-lead ECG	Baseline	1	defined in section 8.1
Coagulation	OLE Part A Week 24	169	[1, 253]
	OLE Part A Week 48	337	(253, 421]
	OLE Part A Week 72	505	(421, 589]
	OLE Part A Week 96	673	(589, 757]
	OLE Part B Week 24	841	(757, 925]
	OLE Part B Week 48	1009	(925, 1093]
	OLE Part B Week 72	1177	(1093, 1261]
	OLE Part B Week 96	1345	(1261, 1359]
	Safety Follow-up ⁴	Not applicable	Use nominal visit
Efficacy Assessment⁵			
Part A: same as in Table 13-1			
Part B: see below			

Table 13-2 Analysis Visit Windows for Safety and Efficacy Assessments for the OLE study			
Assessment	Visit¹	Target Study Day	Analysis Visit Window (in study days)²
Spirometry Weight, Height and BMI (and the corresponding z-scores)	Baseline	1	defined in section 8.1
	OLE Part B Week 12	757	(667, 799]
	OLE Part B Week 24	841	(799, 883]
	OLE Part B Week 36	925	(883, 967]
	OLE Part B Week 48	1009	(967, 1051]
	OLE Part B Week 60	1093	(1051, 1135]
	OLE Part B Week 72	1177	(1135, 1219]
	OLE Part B Week 84	1261	(1219, 1303]
	OLE Part B Week 96	1345	(1303, 1401]
	Safety Follow-up ⁶	Not applicable	>1401
CFQ-R	Baseline	1	defined in section 8.1
	OLE Part B Week 24	841	(667, 925]
	OLE Part B Week 48	1009	(925, 1093]
	OLE Part B Week 72	1177	(1093, 1261]
	OLE Part B Week 96	1345	(1261, 1401]
	Safety Follow-up ⁶	Not applicable	>1401
Sweat chloride Lung Clearance Index IRT	Baseline	1	defined in section 8.1
	OLE Part B Week 24	841	(667, 925]
	OLE Part B Week 48	1009	(925, 1093]
	OLE Part B Week 72	1177	(1093, 1261]
	OLE Part B Week 96	1345	(1261, 1401]
FE-1	Baseline	1	defined in section 8.1
	OLE Part B Week 48	1009	(667, 1177]
	OLE Part B Week 96	1345	(1177, 1401]
Notes:			
^{1,2,3} : See Table 13-1 .			
⁴ For safety Assessment, Safety Follow-up analysis visit will be based on nominal Safety Follow-up visit. If a subject doesn't have a nominal Safety Follow-up visit but has a Part A ETT visit with study day >687 or a Part B ETT visit with study day >1359, then the ETT visit will be mapped into Safety Follow-up analysis visit.			
⁵ For efficacy windowing rules, Part A data will only be used to derive Part A analysis visits using the window rules in Table 13-1 . Part B data will only be used to derive Part B analysis visits using the window rules in this table. Note that Safety Follow-up visits from both Parts will be combined for efficacy summary tables.			

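### The first Part B efficacy windows open at Day 668, so a repeated Part B Day 1 record can be reported as Part B Week 12 or Week 24

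*SAP*

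**What the plan says.** SAP Appendix A, Table 13-2, gives these first Part B efficacy windows:

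- (667, 799] for spirometry, weight, height and BMI: Part B Week 12, target Day 757.
- (667, 925] for CFQ-R, sweat chloride, LCI and IRT: Part B Week 24, target Day 841.
- (667, 1177] for FE-1: Part B Week 48, target Day 1009.

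Table 13-3, the extended windows for the Week 144 interim analysis, repeats the first two but omits IRT and FE-1. Neither table has a Part B Day 1 analysis visit. Footnote 5 of Table 13-2 separates the Parts: "Part B data will only be used to derive Part B analysis visits using the window rules in this table". The selection rule in the notes to Table 13-1 begins "The measurement closest to the target day will be used; or" and gives ties to the latest record. A window that holds a single numerical record therefore takes that record.

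Protocol 9.1.1 makes the two visits coincide by default, but allows a gap. With a gap of 0 or 1 calendar day, an assessment already called for at Week 96 need not be repeated. Those with a longer gap "must complete all assessments specified for the Part A Week 96 AND Part B Day 1 Visits" (Protocol Table 3-2, footnote d). Part A dosing is scheduled from "Day 1 through evening before Week 96 Visit" (Protocol Table 3-1).

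The two documents start the efficacy period differently. In Protocol 12.3.1 the period "for each Part will include the time from the first dose of study drug to the last scheduled efficacy visit in the corresponding Part". In SAP 9.3 it starts at the first dose in the whole extension study.

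**The concern.** A Part B Day 1 assessment, FE-1 apart, is scheduled before the first Part B dose. The windows nevertheless let it stand for a visit 12 or 24 weeks into Part B. The SAP avoids this elsewhere. The Part A efficacy windows in Table 13-1 open after Day 1, and the safety rows of Table 13-2 open Part B only after Day 715 or Day 757.

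At stake are the Part B MMRMs, which show whether the effect lasts. SAP 10.3.2.2.2 assumes missing data are missing at random and does not impute them. The window in effect fills a missing first visit with a value taken before any Part B dose. If study drug was not taken during the gap and some effect was lost, the Part B estimate moves towards loss of effect.

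The plan itself makes missing first values possible. A sweat volume below 15 µL is set to missing, LCI is not calculated from one acceptable replicate, and the main spirometry, CFQ-R and growth analyses use clinic data only.

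**Working it through.** **1. Reproduce the bounds.** The target days imply study day = 7 × week + 1, counted from the first extension dose. The text does not define study day, so this is an assumption.

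- Part A Week 96: 7 × 96 + 1 = 673.
- Part B Weeks 12, 24 and 48: 7 × 108 + 1 = 757; 7 × 120 + 1 = 841; 7 × 144 + 1 = 1009.
- The Week 96 visit may be 5 days early: 673 − 5 = 668, the first whole day above 667.

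The windows therefore open on the earliest in-window date for Part A Week 96.

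**2. Who has a separate Part B Day 1 record.** Let g be the days from Part A Week 96 to Part B Day 1.

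- g = 0 or 1: assessments are not repeated. If the shared value is Part A data, footnote 5 keeps it out of Part B, and a missing first visit stays missing.
- g ≥ 2: assessments are repeated. The earliest such record is Day 668 + 2 = 670, or Day 675 if Week 96 was on Day 673.

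**3. When that record is selected.** Assume Week 96 on Day 673 and Part B visits exactly on schedule from Part B Day 1. The Day 1 record falls on 673 + g and the first real visit on target + g.

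- Week 12 group: the real visit is g days from target and the Day 1 record is 84 − g days from it. The real visit is chosen up to g = 42, where the tie goes to the later record and 757 + 42 = 799 is the last day of the window. From g = 43 it lies outside. Day 1 stays inside while 673 + g ≤ 799, so g ≤ 126.
- Week 24 group: the same steps with 168 − g give g ≤ 84, since 841 + 84 = 925. From g = 85 the real visit lies outside, and Day 1 filled the visit at every gap from there to the longest tried, 139 days.
- FE-1: 1009 + g stays within 1177 for every gap tried, so a real Week 48 sample is chosen if it exists.

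| Assessments | First real value missing, no nearer Part B record | First real visit done |
|---|---|---|
| Spirometry, weight, height, BMI | Day 1 becomes Week 12 for g = 2 to 126 | Day 1 becomes Week 12 for g = 43 to 126 |
| CFQ-R, sweat chloride, LCI, IRT | Day 1 becomes Week 24 for g ≥ 2 (tried to 139) | Day 1 becomes Week 24 for g ≥ 85 (tried to 139) |
| FE-1 | Day 1 becomes Week 48 for g ≥ 2 (tried to 139) | Not at any gap tried |

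At g = 2 the substituted record is 84 − 2 = 82 days before the Week 12 target, or 168 − 2 = 166 days before the Week 24 target.

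**4. Does another rule remove the record?** None in the SAP does.

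- SAP 9.3 starts the period at the first extension dose, so the record is inside it.
- Footnote 3 says only how to label a first-dose-day record as pre-dose or post-dose.
- The OLE-FAS in SAP 8.2.3 needs one dose anywhere in the extension, whereas Protocol 12.2 needs a dose in the Part.
- Protocol 12.3.1 would exclude the record, but SAP 3.1 declares only the pooling of safety data as a change to the protocol.

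**5. Would midpoint bounds be enough?** The midpoints are (673 + 757)/2 = 715, (673 + 841)/2 = 757 and (673 + 1009)/2 = 841. They remove Day 1 for gaps up to 42 days (Week 12 group) and 84 days (Week 24 group). It still enters at longer gaps.

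**The case against.** The strongest reply is that the route is narrow. By default Part A Week 96 is Part B Day 1 and no repeat is made. Substitution at short gaps needs a gap over 1 day, a missing first value and no nearer Part B record. An in-window early-termination visit or unscheduled record can displace Day 1. Protocol 9.1.2 waives the Safety Follow-up Visit for a transition to another Part within 28 days of the last dose, which suggests short gaps were expected. Efficacy is secondary, with no formal decision rule. Most assessments at every visit are pre-dose, and the efficacy analysis includes values after discontinuation by design. A Day 1 value after a short gap still reflects the parent study and 96 weeks of Part A.

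All of this limits reach and size. It does not make the rule right: the record still precedes any Part B dose, and no maximum gap is stated.

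A reader might infer three stronger points that the documents do not support:

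- That every subject with a missing first Part B value is affected. This would hold only if a shared Week 96/Day 1 record counted as Part B data, which the SAP leaves unsaid.
- That the substituted values are often off drug. The dosing schedule makes this possible during a gap, but no gap frequency or length is given.
- That the Week 48 MMRM estimates are contaminated by this route. The only first window aimed at Week 48 is for FE-1, which is summarised descriptively and may be sampled after dosing. IRT is also descriptive.

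**Conclusion.** The defect holds for subjects with a gap of more than 1 calendar day. Followed as written, the SAP can report a record from before the first Part B dose as Part B Week 12 or Week 24, and enter it in the MMRM for every endpoint in those groups except IRT. At long gaps it does so although the real visit took place. The direction is towards loss of effect only if effect was lost during the gap.

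The number affected cannot be derived. It lies between 0 and 64, where 64 is enrolment in the whole extension study and so only an upper limit for Part B. The shift per subject can only be illustrated. A substituted value that differs by d from the true one moves a raw mean of N subjects by d/N. Assuming d from 0 to 60 mmol/L for sweat chloride and N from 40 to 64, that is 0 up to 60/64 = 0.94 or 60/40 = 1.5 mmol/L. The top of the range assumes complete loss of a 60 mmol/L effect. It concerns a raw mean, not the MMRM estimate, and should not be read as an expected bias. The gap thresholds assume Week 96 on Day 673 and on-schedule Part B visits.

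**What to change.** - In Tables 13-2 and 13-3, require any record used for a Part B efficacy analysis visit to be dated after the first Part B dose date. This mirrors the lower bound of 1 in the Part A rows. Changing 667 to a midpoint is not enough, for the reason in step 5.
- State that a record shared by Part A Week 96 and Part B Day 1 counts as Part A data.
- Align SAP 9.3 with Protocol 12.3.1, so that the Part B efficacy period starts at the first Part B dose.

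The cost is SAP wording and one programming condition. A few first Part B values become missing, which the MMRM already handles under missing at random. At long gaps the first Part B analysis visit will be empty although a visit was made, because the target days run on from Part A. This change does not cure that.
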